## **9.2 Reporting to the Sponsor and/or Federal Agencies**

### **9.2.1 Notification of Federal Agencies by Investigator**

Copies of all correspondence to the St. Jude IRB, including serious adverse event reports, are provided to the St. Jude Office of Regulatory

Affairs via the electronic reporting system (TRACKS). All FDA related correspondence and reporting will be conducted through the Regulatory Affairs Office.

The FDA will be notified in writing (IND safety report) of any serious and unexpected adverse event associated with an investigational treatment or device. Annual reports, which will include the up-to-date clinical and safety data, will be submitted to the FDA at least annually.

#### **9.2.2 Recording Adverse Events and Serious Adverse Events**

Adverse events will be evaluated and documented by the clinical staff and investigators. The CRAs are responsible for documenting adverse events and entering them into the CRIS protocol-specific database. AEs that are classified as serious, unexpected, and at least possibly related will be reported expeditiously to the St. Jude IRB as described in protocol section 9.1. All other events will be reported to the IRB as part of the continuing review process.

As stated in section 7.2, only new or worsening problems occurring after the administration of study drug will be reported as adverse events, as sickle cell patients may have pre-existing conditions that fall in the range of toxicity per the CTCAE and are not related to study drug (e.g. anemia, fever, pain). Any event occurring more than 72 hours after administration of study drug will not be captured.

### **9.3 Emergency Unblinding**

In the case of a medical emergency or in the event of a serious medical condition, when knowledge of the investigational product is essential for the clinical management or welfare of the subject, an investigator or other physician managing the subject may decide to unblind that subject's treatment code.

The physician managing the medical emergency or serious condition should attempt to contact the principal investigator to discuss options prior to unblinding, and the principal investigator should approve the unblinding, when applicable. However, ensuring patient safety is the primary objective when the decision to unblind the treatment assignment is made.

The principal investigator or designated study personnel will complete an order in MILLI with the request to unblind the patient's treatment arm. The principal

investigator or treating clinician will contact pharmacy to receive the unblinding information.

All occurrences of emergency unblinding will be reported to the IRB according to the criteria established in protocol section 9.0, and the FDA, when applicable. In a majority of cases, emergency unblinding will occur while managing a serious adverse event (SAE), and will therefore be reported with the SAE. If the unblinding event is not directly associated with an SAE, the same timeline and mechanism for reporting SAEs will be used to notify the IRB of the event (section 9.1).

## **10.0 DATA COLLECTION, STUDY MONITORING, AND CONFIDENTIALITY**

### **10.1 Data Collection**

Members of the clinical care team will complete documentation in the electronic medical record for each study encounter. Data will then be abstracted into a secure database by study staff, which serves as the electronic case report forms (eCRFs). Records from the study which identify the study participant will be kept confidential in a secured area.

### **10.2 Study Monitoring**

Source document verification of eligibility for all SJCRH cases will be performed within two weeks of completion of enrollment. This will include verification of appropriate documentation of consent. Monitoring of timeliness of serious adverse event reporting will be done as events are reported in TRACKS.

Monitoring of this protocol is considered to be in the High Risk 3 category. The Monitoring Plan is outlined in a separate document from this protocol, but has been submitted for review and approval by the Clinical Trials Scientific Review Committee and the Institutional Review Board.

Continuing reviews by the IRB and CT-SRC will occur at least annually. In addition, SAE reports in TRACKS are reviewed in a timely manner by the IRB/ OHSP.

### **10.3 Confidentiality**

Source documents from the study which identify the participant will be kept confidential in a secured area and a password-protected database. Any list containing the study number and the medical record number will be maintained in a password-protected electronic file and will be destroyed after all data have been analyzed.

The medical records of study participants may be reviewed by the St. Jude IRB, FDA, clinical research monitors, and other authorized regulatory personnel.

## **11.0 STATISTICAL CONSIDERATIONS**

This is a double-blind placebo-controlled clinical trial evaluating the effect of gabapentin when added to standard pain management for patients with sickle cell disease experiencing acute pain crisis in the ambulatory care setting. The primary study objective is to assess the analgesic efficacy of gabapentin for pain during VOC in participants with SCD, by comparing the proportion of participants with a decrease of  $\geq 33\%$  in pain scores between presentation to the acute care setting and assessment at 3 hours post administration of study drug, in the gabapentin and placebo groups. The intention-to-treat principle will be followed and all eligible, randomized subjects will be analyzed in the primary analysis as randomized.

### **11.1 Sample size**

Retrospective review of 26 months of records (August 1, 2010 to October 1, 2012) indicated that 137 patients, ages 1-18, experienced VOC due to SCD and were administered opioids. We analyzed the pain scores from a subset of 40 patients between the ages of 8 and 18 who had received opioid(s) and also had pain scores documented at baseline and end of the visit. We found a reduction in the pain scores from baseline to discharge or admission of  $\geq 33\%$  [81-83] in 45% of patients (18/40). The hypothesis is that treatment with gabapentin has better analgesic efficacy than placebo in the treatment of pain during VOC, when added to the current standard of care for pain during VOC which comprises opioids and non-steroidal anti-inflammatory drugs. An increase in the proportion of patients with  $\geq 33\%$  reduction of the pain scores from 45% to at least 65% between presentation and assessment at 3 hours post administration of study drug is considered clinically meaningful [81-83].

Let  $P_t$  and  $P_c$  be the proportions of participants with a decrease of  $\geq 33\%$  in pain scores between presentation to the acute care setting (ACS) and 3 hours post study drug administration, in the gabapentin and placebo groups,

respectively. We wish to test whether there is a significant difference in the proportions of participants with a decrease of  $\geq 33\%$  in pain scores in two groups and formulate the following hypothesis: the null hypothesis  $H_0: \Delta = P_t - P_c = 0$  against the 1-sided alternative hypothesis  $H_1: \Delta > 0$ . With the design parameters of a type I error rate ( $\alpha$ ) of 0.05 and a type II error rate ( $\beta$ ) of 0.2, assuming one interim analysis and  $\Delta = 0.2$  under  $H_1$ , we will need a total of 166 patients (83 per group) for our two sample test. The interim analysis will be conducted to assess efficacy and futility, when there are 96 subjects randomized. We will recommend that the trial will be halted for efficacy (in favor of  $H_1$ ) if the nominal p-value for the interim analysis is less than or equal to 0.0143. We will recommend the trial should be halted for futility (in favor of  $H_0$ ) if the nominal p-value for the interim analysis is greater than or equal to 0.2249. If  $H_0$  is true, this interim analysis has a 79% probability of stopping in favor of  $H_0$ . If  $H_1$  is true, this interim analysis has a 53% probability of stopping in favor of  $H_1$ . To account for the planned interim analysis, the final analysis will be at the nominal p-value of 0.0447; thus maintaining the overall type I error rate at 0.05. This plan is based on the binomial two-sample difference in proportions with a non-binding interim analysis based on power family spending functions with alpha and beta spending parameters set to 0.1 (EAST software v5.3).

**Accrual:** Based on the retrospective data, we can expect to prospectively evaluate 63 patients for enrollment per year. If we enroll and randomize 2/3 of the eligible patients, the enrollment would reach 42 patients per year. Therefore, it will take approximately four years to enroll all 166 patients necessary to address the primary objective.

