## 11.2 Randomization

Eligible patients with an established diagnosis of pain and VOC will be consented and randomized to receive a single dose of gabapentin or placebo. Morphine or other opioid and non-steroidal anti-inflammatory drugs will be available to both groups as needed for pain and will be administered according to the current standard of care for pain in VOC from the Department of Hematology. Randomization will be performed in SJCRH pharmacy by a pharmacist, using the randomization program developed by the Department of Biostatistics. The randomization will be stratified by three age categories (1-3yr, 4-6yr,  $\geq 7$ yr) for which distinct pain assessment tools are applied and for 2 pain scores categories at assessment at presentation: 4- 6 and 7-10, respectively. A

block randomization with block sizes varying randomly between 4 and 6 will be used in each stratum.

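### Section 11.1 gives total interim stopping probabilities as if they ran in one direction: under H1 the chance of an efficacy stop is about 43%, not 53%

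*Combined protocol and SAP*

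**What the plan says.** Section 11.1 plans one interim analysis, "when there are 96 subjects randomized", out of 166 in total. The test is one-sided.

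- **Efficacy:** "We will recommend that the trial will be halted for efficacy", which the plan glosses as in favor of H1, if the nominal p-value is 0.0143 or less.
- **Futility:** "We will recommend the trial should be halted for futility", glossed as in favor of H0, if the nominal p-value is 0.2249 or more.
- **Final analysis:** nominal p-value of 0.0447, for an overall type I error of 0.05.

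Two operating characteristics follow. The first takes the null hypothesis as true and gives a 79% chance of a stop favoring it. The second takes the alternative as true; its wording is "this interim analysis has a 53% probability of stopping in favor of", completed by the symbol for the alternative. The probability of stopping in the wrong direction is not given under either hypothesis.

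The alternative is a difference of 0.20. The same section describes it as a rise in the proportion of patients with at least a 33% "reduction of the pain scores from 45% to at least 65" percent. The plan is called a "non-binding interim analysis based on power family spending functions with alpha and beta spending parameters set to 0.1".

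**The concern.** Because the paragraph itself equates a stop in favor of H1 with crossing the efficacy boundary, 53% has to be read as the chance of an early efficacy stop when the drug works as assumed. At 96 of 166 patients, a one-sided cutoff of 0.0143 looks too strict for that. The expected Z at the interim is about 2.01 and the cutoff is 2.19, so the chance of crossing must be below one half.

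Two things are at stake. Readers are told that early success is more likely than not under H1, when it is less likely than not. And the chance that an effective drug draws a futility recommendation is missing, with its probability apparently counted within a figure labelled as favoring H1. Since the stopping rule is a non-binding recommendation, whoever weighs a futility signal would want that number.

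**Working it through.** **Inputs, all from section 11.1.** Response 45% on placebo and 65% on gabapentin; 96 patients at the interim and 166 (83 per arm) at the end; one-sided nominal p-values of 0.0143, 0.2249 and 0.0447. Assumed: 48 per arm at the interim, all outcomes observed.

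**Boundaries on the Z scale.** 0.0143 gives 2.189 (efficacy), 0.2249 gives 0.756 (futility), 0.0447 gives 1.699 (final). The information fraction is 96/166 = 0.578.

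**Does the rest of the design reproduce?** The variance sum under H1 is 0.65 × 0.35 + 0.45 × 0.55 = 0.475. The expected Z is 0.2/√(0.475/48) = 2.010 at the interim and 0.2/√(0.475/83) = 2.644 at the end. A bivariate normal with correlation √0.578 gives:

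- type I error 0.0500 with the futility rule ignored, as a non-binding rule requires;
- power 80.1% with the futility rule followed (83.4% with it ignored).

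So the sample size, alpha, power and printed boundaries fit together.

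**Interim stopping under H1**

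| Method | Efficacy | Futility | Total |
|---|---|---|---|
| Normal, unpooled variance | 42.9% | 10.5% | 53.4% |
| Normal, null variance for the cutoff, alternative variance for the spread | 41.1% | 10.8% | 51.9% |
| Exact binomial, pooled Z | 42.8% | 10.1% | 53.0% |

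For the first row: P(efficacy) = P(Z ≥ 2.189 − 2.010) = 0.429 and P(futility) = P(Z ≤ 0.756 − 2.010) = 0.105. None of the three methods puts the efficacy stop near 53%; the first and third totals round to 53%.

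**Interim stopping under H0.** By the normal approximation, futility is 1 − 0.2249 = 77.5% and efficacy is 1.4%, in total 78.9%, which rounds to the printed 79%. The futility figure alone rounds to 78%.

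**Could unequal arms or missing outcomes explain 53%?** Section 11.2 has three age groups by two pain categories, that is six strata, with "block sizes varying randomly between 4 and 6 will be used in each stratum". An incomplete block of 6 can leave a stratum at most 3 patients out of balance, so the overall difference is at most 6 × 3 = 18. Over every split from 39/57 to 57/39 and all three methods, the efficacy stop stays between 39% and 44% and the futility stop between 10% and 12%. Missing outcomes lower the efficacy figure: with 43 evaluable per arm (an illustration, about 10% missing) it is 36% to 39%.

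**What would make 53% right as an efficacy probability?** By the unpooled normal calculation, any one of these: 61 per arm (122 patients) at the interim, a cutoff of 0.0265, or a true difference of 0.223. The plan states none of them.

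**The case against.** The best case for leaving the text alone is that nothing depends on it. Stopping is set by the p-value cutoffs, the outcome is a non-binding recommendation, and neither percentage feeds the sample size, the accrual estimate or any analysis. The futility risk is also already inside the stated power. All of this stands, and it is why the point is minor. It does not make the sentence correct.

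The cause is inferred, because the design output is not in the documents. Another quantity also comes close to 53%: the share of all H1 rejections that happen at the interim, 0.429/0.8015 = 53.5%. That idea does not yield 79% under H0, whereas total stopping fits both printed figures on the normal calculation. Total stopping is therefore the likelier explanation, but not a proven one. On either reading the sentence as worded is wrong.

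The H0 figure is weaker evidence. Exact enumeration at 45% in both arms gives 76.4% futility plus 1.5% efficacy, or 77.9%, which rounds to 78% rather than 79%. The H0 sentence is best treated as support for the diagnosis and tidied at the same time, not counted as a second error of substance.

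**Conclusion.** The concern holds. At the plan's own rates and boundaries, the probability of an efficacy stop at the interim under H1 is about 43% (41% to 43% across methods), against a printed 53%. The unstated probability of a futility stop under H1 is 10% to 11%. Under H0 the normal approximation gives 77.5% futility and 1.4% efficacy, against a printed 79% for futility alone.

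This rests on 48 per arm with complete outcomes. No split that the blocking allows brings the efficacy stop above about 44%, and missing data reduce it. Mislabelled totals are the most plausible cause. The error is confined to two descriptive sentences: 166 patients, the boundaries, overall alpha and 80% power are unaffected.

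**What to change.** Replace the two probability sentences in section 11.1 with wording such as:

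> Under H0, the interim analysis has about a 78% probability of stopping for futility and 1.4% of stopping for efficacy (79% in total). Under H1, it has about a 43% probability of stopping for efficacy and 10% of stopping for futility (53% in total).

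State that these are normal-approximation figures for 48 per arm, and confirm them against the design output.

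One query can be settled in the same look-up. The plan names power family spending functions with parameters of 0.1 but does not define the family. Read as a spending exponent, 0.1 would spend 0.05 × 0.578^0.1 = 0.0473 at the interim. Read as a Wang-Tsiatis shape, it gives 0.0165 and 0.0434. Neither returns the printed 0.0143 and 0.0447. This does not show an error, since the printed boundaries do hold alpha at 0.0500, but the sponsor should confirm the family and parameters.

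The cost is two sentences and one check of existing output. The stated chance of early success becomes less favorable; patient numbers, boundaries, alpha and power do not change.

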### **11.3 Statistical analysis**

#### **11.3.1 Primary Objective**

To assess the analgesic efficacy of gabapentin (vs. placebo) for pain during VOC in participants with SCD. A response to study drug will be defined by a decrease in pain score of  $\geq 33\%$  between presentation to the acute care setting and assessment at 3 hours post administration of study drug.

For each patient, if the reduction of the pain scores between presentation to the acute care setting and 3 hours post administration of study drug is 33% or greater, then this patient will be defined as having a successful intervention. The proportions of successful interventions in the gabapentin and placebo groups will be estimated and compared using Z-test (PROC FREQ procedure in SAS).

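### The thresholds 0.0143 and 0.0447 hold the one-sided error at 0.05 only in the large-sample approximation; with the planned Z-test, equal arms and futility overridden, the exact figure at 45% is about 0.056

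*Combined protocol and SAP*

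**What the plan says.** Section 11.1 tests for a difference in response proportions "against the 1-sided alternative hypothesis", with 83 participants per group and one interim look at 96 randomized. At the interim, a nominal p of 0.0143 or less leads to a recommendation to stop for efficacy, and a p of 0.2249 or more to a recommendation to stop for futility. For the end of the trial the section states that "the final analysis will be at the nominal p-value of 0.0447; thus maintaining the overall type I error rate at 0.05". It describes the scheme as a "non-binding interim analysis based on power family spending functions".

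The control rate comes from a chart review that found the response "in 45% of patients (18/40"), and the target is an increase "from 45% to at least 65% between presentation and assessment at 3 hours post administration of study drug is considered clinically meaningful".

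Section 11.3.1 says that the two proportions "will be estimated and compared using Z-test (PROC FREQ procedure in SAS"). It mentions no continuity correction and no exact test, and does not say whether the variance is pooled. No exact operating characteristics are given anywhere. Section 11.2 randomizes within six strata (three age groups by two presenting-pain categories) in blocks of 4 to 6.

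**The concern.** The type I error is stated without qualification as a property that the design maintains, and any efficacy claim rests on it. Normal-theory thresholds control the error of a continuous statistic. The statistic here takes discrete values: with 83 per arm, one more responder in the lead moves the nominal p-value by well over 0.01 near the rejection boundary. If 0.0447 falls just above one of those steps, the test rejects more often under the null hypothesis than the nominal figure suggests.

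Because the futility rule is non-binding, the stated 0.05 has to hold even when a futility recommendation is overridden. Early futility stops cannot be counted towards controlling it.

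**Working it through.** **Inputs.** From 11.1: interim at 96, taken as 48 per arm (an assumption); final at 83 per arm; efficacy thresholds 0.0143 (z = 2.189) and 0.0447 (z = 1.699); futility threshold 0.2249; null rate 45% in both arms; alternative 45% against 65%. From 11.3.1: an uncorrected Z-test. All randomized subjects are assumed to have the 3-hour outcome.

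**Step 1. Reproduce the plan's 0.05.** With information fraction 96/166 = 0.578, the two statistics have correlation √0.578 = 0.760. Ignoring futility, the error is 0.0143 + 0.0447 − P(both cross) = 0.0590 − 0.0090 = **0.0500**. The stated figure is reproduced.

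**Step 2. The step in the discrete test.** The pooled statistic is Z = (x_t − x_c)/n ÷ √(2p̄(1 − p̄)/n).
- 43 against 32 responders of 83: p̄ = 75/166 = 0.452, difference 11/83 = 0.1325, standard error 0.0773, Z = 1.716, p = 0.0431.
- 47 against 36: p = 0.0439.
- Lead of 10 (42 against 32): p = 0.0592.

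Near the planning rate, then, 0.0447 sits just above the p-value for a lead of 11. At a common rate of 45%, the final look taken alone has a true rejection probability of 0.0506, not 0.0447. The interim look has 0.0154, not 0.0143.

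**Step 3. Exact two-stage error.** Enumerate all outcomes at 48/48, carry forward those that did not cross for efficacy, add 35 per arm, and sum the probability of rejection. At 45% with futility overridden, this is 0.0154 at the interim plus 0.0405 at the final look among trials that had not already stopped, or 0.0559.

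| Common rate | Futility overridden | Futility followed |
|---|---|---|
| 40% | 0.0532 | 0.0479 |
| 45% | 0.0559 | 0.0503 |
| 50% | 0.0569 | 0.0512 |

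Unpooled variance gives 0.0560 at 45%, and a simulation of two million trials gives 0.0558. Over common rates of 20% to 80% the futility-overridden error is 0.0495 to 0.0569. A continuity correction, which the plan does not mention, would bring it to 0.039 at 45%.

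**Step 4. Unequal final arms.** Pooled test, 48/48 at interim, futility overridden, gabapentin arm first:

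| Final split | 40% | 45% | 50% |
|---|---|---|---|
| 80/86 | 0.0477 | 0.0485 | 0.0517 |
| 81/85 | 0.0460 | 0.0479 | 0.0525 |
| 82/84 | 0.0561 | 0.0574 | 0.0569 |
| 84/82 | 0.0510 | 0.0545 | 0.0569 |
| 85/81 | 0.0503 | 0.0527 | 0.0525 |
| 86/80 | 0.0497 | 0.0515 | 0.0517 |

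The range is about 0.046 to 0.057, on both sides of 0.05.

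**Step 5. A lower final threshold at 83/83.**

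| Final threshold | Error, 40% / 45% / 50% (overridden) | Power, futility followed | Power, overridden |
|---|---|---|---|
| 0.0447 | 0.0532 / 0.0559 / 0.0569 | 0.808 | 0.840 |
| 0.042 | 0.0495 / 0.0459 / 0.0444 | 0.785 | 0.811 |
| 0.040 | 0.0448 / 0.0435 / 0.0439 | 0.779 | 0.803 |

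At 0.042 the error does not exceed 0.0499 for any common rate from 10% to 90%.

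**The case against.** The strongest reply is that nothing was miscalculated. The printed thresholds give 0.0500 under standard group-sequential theory, and every uncorrected Z-test on binomials departs from its nominal level in finite samples. This stands. A reader might infer a slip in arithmetic or in the use of the software, and the documents do not support that.

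A second reply is that the figure depends on arms the design does not guarantee. Incomplete blocks in six strata leave small imbalances. In a simulation with assumed stratum shares of 5, 5, 8, 7, 35 and 40%, exactly 83/83 occurred in about 32% of trials. This also stands, and Step 4 shows the error can then fall below 0.05.

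Third, the enumeration gives every patient the same response probability. Stratified allocation analysed with an unadjusted test becomes conservative when the strata are prognostic. In simulations of 60,000 trials with futility overridden, two runs gave 0.055 to 0.056 with all strata at 45%. Setting the lower and higher pain categories at 55% and 35% gave 0.051 to 0.052, 60% and 31% gave 0.047, and 65% and 27% gave 0.040 to 0.043. The stratum rates are assumptions, since the documents report none, but the direction is right.

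Finally, the excess largely disappears if the futility recommendation is followed, and nothing in the plan suggests that an override is expected. That limits the consequence. It does not rescue the unqualified claim, because a rule declared non-binding has to control the error without it.

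**Conclusion.** The point holds as a qualification of a stated design property. At the plan's own rate and allocation, the exact one-sided error is about 0.056 against the stated 0.05, an excess of about 0.006. This rests on an uncorrected Z-test, arms of 48/48 then 83/83, a homogeneous response rate, complete outcomes and an overridden futility recommendation. With the recommendation followed it is about 0.050 at 45%. The choice of pooled or unpooled variance does not matter at equal arms.

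A reader might infer that the trial as designed always exceeds 0.05. The documents do not support that: modest imbalance between arms or prognostic strata can take the error below 0.05. The matter is minor for a phase II trial and worth correcting mainly because correction is cheap.

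**What to change.** Restate 11.1 to say that 0.05 is the large-sample value, and that under equal arms and a common 45% rate the exact one-sided error of the planned Z-test is about 0.056 if the futility recommendation is overridden and about 0.050 if it is followed. This costs a sentence and changes neither sample size nor power.

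Optionally, if strict control is wanted, there are two routes:
- Use a final p-value enumerated at the actual arm sizes, which also handles imbalance.
- Lower the final threshold to about 0.042, which keeps the exact error at 0.044 to 0.049 at 83/83 for rates of 40% to 50%. At 45% against 65%, power falls from 0.81 to 0.785 with futility followed, or from 0.84 to 0.81 without. The first of these drops below the planned 80%. A threshold of 0.040 is stricter than needed at 83/83.

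Either route should be fixed before the interim data are seen.
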